IMP	
GEN3009 will be administered intravenously in 4-week cycles (ie., 28 days).
 
In the Dose Escalation, the starting dose is █ mg. Ten DLs may be tested. Additional/intermediate DLs may also be explored based upon emerging data.
 
In the Expansion, █ mg and the RP2D of GEN3009 will be investigated together with GEN3013 at 48 mg.
 
GEN3013 will be administered s.c. in 4-week cycles (ie., 28 days).

	In the Expansion, 48 mg of GEN3013 will be investigated together with GEN3009 at CC1 mg and the RP2D.
Statistics	In the Dose Escalation, MTD and/or RP2D will be determined using a modified Bayesian Optimal Interval (mBOIN) design. Expansion of GEN3009 monotherapy will be conducted in 3 indications with a maximum sample size of 20 per indication. Expansion of GEN3009 in combination with GEN3013 will be conducted in 1 indication following a safety run-in phase with a maximum sample size of 32 for the cohort. No formal statistical hypothesis testing will be performed. AEs will be described using summary statistics. Individual curves of plasma concentration for GEN3009 or GEN3013 will be presented for all subjects. PK parameters will be calculated based on non-compartmental methods and calculated separately. The revised response criteria (Cheson et al., 2014) will be used to assess the response for B-cell NHL and the International Workshop on Chronic Lymphocytic Leukemia (Hallek et al., 2018) for CLL.

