4 TRIAL DESIGN

4.1 Description of Trial Design

This trial is a FIH, open-label, multicenter trial to evaluate the safety, tolerability, PK, pharmacodynamics, immunogenicity, and preliminary efficacy of GEN3009 (DuoHexaBody®-CD37) as a single agent and in combination with GEN3013 (DuoBody®-CD3xCD20, epcoritamab) in subjects with R/R B-cell NHL.

The trial will be conducted in 2 parts, Dose Escalation and Expansion. Up to 90 subjects with R/R B-cell NHL will be enrolled in the Dose Escalation, and approximately 92 subjects will be enrolled in the Expansion as follows:

- GEN3009 monotherapy cohorts: R/R DLBCL (N=20), R/R FL (N=20), and R/R CLL (N=20)
- GEN3009 + GEN3013 combination cohorts: safety run-in phase in R/R DLBCL or R/R FL (N=6-12) followed by Expansion phase in R/R DLBCL(N = 20).

For GEN3009 monotherapy cohorts , GEN3009 will be administered IV in 4-week cycles (ie, 28 days), with a schedule of weekly dosing in Cycles 1 through 3, every second week in Cycles 4 through 9, and every 4 weeks in Cycle 10 until disease progression, unacceptable toxicity, death or end of trial.

For GEN3009 + GEN3013 combination cohorts, GEN3009 will be administered IV in 4-week cycles (ie, 28 days), with a schedule of weekly dosing in Cycles 1 through 3, and every 4 weeks in Cycles 4 through 12 until up to a maximum of 12 cycles or any discontinuation criteria met (see Section 8), whichever occurs earlier. GEN3013 will be administered subcutaneously (s.c.) in Cycles 1 (starting from C1D8) through 3 , and then every 4 weeks in Cycles 4 through 12 until up to a maximum of 12 cycles or any discontinuation criteria met, whichever occurs earlier (see Table 21). After completion of Cycle 12, subjects who are in SD or better will have the option to continue receiving GEN3013 every 4 weeks until any discontinuation criterion is met.

Table 21 Dose and Schedule

GEN3009 IV as assigned	GEN3013 s.c.
DL1: CCI mg	DL1: 48 mg
DL2: RP2D	
• Cycles 1-3: Days 1, 8, 15, 22• Cycles 4-12: Day 1 
• Cycle 1:
◦ 0.16 mg (priming dose) on Day 8◦ 0.8 mg (intermediate dose) on Day 15◦ 48 mg (full dose) on Day 22• Cycles 2 and 3: 48 mg on Days 1, 8, 15, and 22• Cycles 4-12: 48 mg on Day 1 
After completion of Cycle 12:
 
• Subjects who are in SD, PR or CR:
◦ Every 4 weeks (Cycles 13, 14, 15+): 48 mg on Day 1

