4.4.3 Trial Stopping Rules

If any of the events listed below occur, a prompt cumulative review of safety data will be conducted by the DMC to determine whether the trial should be discontinued permanently.

- Events outside of the DLT window, in the Dose Escalation part and in the expansion part of the trial, that in the judgment of the sponsor are deemed serious enough to warrant an immediate comprehensive evaluation by the SC;
- If at any time, all DLs are considered unsafe as defined by the mBOIN;
- Any safety finding assessed as related to GEN3009 and/or GEN3009 + GEN3013 combination treatment that, in the opinion of the DMC, contraindicates further dosing of trial subjects.

Any recommendation of the DMC must be approved by the sponsor SC.

In addition, to ensure subject safety, the following stopping criteria are applicable to subjects who have completed the DLT period during the Dose Escalation, as well as subjects enrolled in Expansion:

- $\geq 33\%$ of subjects experiencing Grade 3 or greater treatment-emergent IRRs, or
- $\geq 33\%$ of subjects experiencing Grade 4 neutropenia lasting >7 days not attributable to underlying disease, or
- $\geq 33\%$ of subjects experiencing Grade 3 or greater CRS or ICANS.

As noted in Section [10.8](#), the DMC will review the totality of the data and monitor safety for the trial on a quarterly basis or more frequently during the Dose Escalation and at pre-specified intervals during the Expansion (including safety run-in) as defined in the DMC charter.

For each individual subject who has already received GEN3009 or GEN3009 + GEN3013 combination and is currently in the trial at the time the trial stopping criteria are met, the benefit-risk whether to stop or continue treatment will be assessed. To allow continuation of treatment, DMC consultation will be considered. All subjects continuing GEN3009 or GEN3009 + GEN3013

combination after trial termination should continue to have investigator follow-up for safety until the subject's condition returns to baseline or until the start of a new anti-cancer therapy, whichever comes first.

Where applicable, regulatory authorities and independent ethics committees (IECs)/institutional review board (IRBs) will be notified of any significant actions taken with the trial.

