7.4.3.2 Cytokine Release Syndrome (the GEN3009 + GEN3013 Combination Cohort)

CRS has been reported with the use of GEN3013. To date, CRS is not a known/identified risk with GEN3009. Refer to Section 7.5.2 and Appendix 13 for guidelines for grading and supportive care for CRS management.

CRS must be graded according to the ASTCT grading for CRS (Lee et al., 2019).

Table 26 GEN3013 Dose Modification for Cytokine Release Syndrome (GEN3009 + GEN3013 Combination Cohort)

CRS	
ASTCT Grade	Dose Modification
Grade 1	
Hold GEN3013 (and GEN3009 if given in combination) until resolution of CRS event and treat the subject (see Appendix 13)
Grade 2	
Hold GEN3013 (and GEN3009 if given in combination) until resolution of CRS event and treat the subject.If Grade 2 or higher CRS occurs with the second full dose or beyond, administer CRS prophylaxis with the next dose until a GEN3013 dose is given without subsequent CRS (of any grade)
Grade 3 lasting less than 72 hours	
Hold GEN3013 (and GEN3009 if given in combination) until resolution of CRS event and treat the subject.Continue with the next planned GEN3013 dose at the planned date and hospitalize the subject for at least 72 hours following this GEN3013 administration.If Grade 2 or higher CRS occurs with the second full dose or beyond, administer CRS prophylaxis with the next dose until a GEN3013 dose is given without subsequent CRS (of any grade)
Grade 3 lasting longer than 72 hours	
Permanently discontinue administration of GEN3013 and treat the subject (see Appendix 13)
Grade 3, second occurrence (ie, 2 separate Grade 3 events)	
Permanently discontinue administration of GEN3013 even if each event resolved to Grade 2 within 72 hours, and treat the subject (see Appendix 13)
Grade 4 CRS	
Permanently discontinue administration of GEN3013 and treat the subject (see Appendix 13)

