11.11 Sample Size Calculation

Sample size for the Dose Escalation is expected to be up to 90 subjects based on simulations of the mBOIN design in order to provide adequate information for MTD estimation and the planning and design of future trials. The expected number of subjects depends on the true relationship between dose and DLT probability but is expected to lie between 30 to 40 subjects in realistic scenarios. Approximately 49 additional subjects may be recruited to DLS below the MTD where it is found relevant to further explore the PK, toxicity, and efficacy.

Table 34 shows 4 different scenarios for the probability of a subject having a DLT at the 10 DLs. For each scenario the total expected number of subjects, when following the mBOIN design, is shown in the rightmost column. The mBOIN design method behaves as intended with most subjects exposed to the DLs with DLT probability close to the target DLT rate and fewer subjects exposed in total if the toxicity is high at the lowest DLs.

Table 34 Modified BOIN Design Characteristics

Simulation Scenario		Probability of DLT, Expected Number of Subjects at Each Dose Level										Expected Number of Subjects
		1	2	3	4	5	6	7	8	9	10	
1	Prob(DLT)	0%	1%	1%	2%	3%	4%	5%	10%	20%	30%	
	Num of subjects	1.0	1.1	1.1	3.2	3.4	3.5	3.8	5.1	5.9	4.6	32.7
2	Prob(DLT)	0%	1%	1%	2%	3%	4%	5%	20%	25%	35%	
	Num of subjects	1.0	1.1	1.1	3.3	3.4	3.5	4.9	6.2	4.7	2.9	32.0
3	Prob(DLT)	0%	1%	1%	2%	3%	4%	5%	20%	40%	60%	
	Num of subjects	1.0	1.0	1.1	3.3	3.3	3.5	5.0	7.3	4.8	1.0	31.3
4	Prob(DLT)	0%	1%	1%	2%	3%	4%	5%	10%	12%	15%	
	Num of subjects	1.0	1.0	1.1	3.2	3.4	3.5	3.8	4.3	4.4	6.6	32.2

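### The 33% stopping criterion for Grade 3 or higher CRS/ICANS is not restricted to subjects given GEN3013, and on its stated population it can hardly, or never, be met

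*Protocol*

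**What the plan says.** Protocol Section 4.4.3 lists three criteria, each with a 33% threshold: Grade 3 or higher IRRs, prolonged Grade 4 neutropenia, and at least 33% "of subjects experiencing Grade 3 or greater CRS or ICANS". One sentence sets the population for all three: "the following stopping criteria are applicable to subjects who have completed the DLT period during the Dose Escalation, as well as subjects enrolled in Expansion". The CRS/ICANS line adds no restriction by cohort, regimen or GEN3013 exposure, and gives no time of evaluation.

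On numbers, Section 4.1 says: "Up to 90 subjects with R/R B-cell NHL will be enrolled in the Dose Escalation, and approximately 92 subjects will be enrolled in the Expansion". Three Expansion cohorts of 20 receive GEN3009 alone. The combination has a run-in of 6 to 12 subjects and then 20 with DLBCL. The Synopsis says this Expansion is run in one indication "following a safety run-in phase with a maximum sample size of 32 for the cohort".

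On who is at risk, Section 7.4.3.2 states: "To date, CRS is not a known/identified risk with GEN3009". Section 7.4.3.4 says the same of ICANS. Section 10.3 lists CRS and ICANS as events of special interest for GEN3009 + GEN3013 only.

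**The concern.** A percentage rule detects a problem only if the people in its denominator can have the event. Here the stated population is mostly people who never receive the drug that the protocol links to CRS and ICANS. Each of them dilutes the rate and, on the protocol's own account, is not expected to add an event. Section 4.1.2 has the Expansion cohorts enrolling in parallel, so this dilution is the planned course of the trial.

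Section 2.3.2 names CRS and ICANS as the main risks of GEN3013. If the text is followed as it stands, the trial-level numeric criterion for those risks could stay unmet however toxic the combination proved to be.

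**Working it through.** **Inputs.** Escalation: up to 90 (Section 4.1). Section 11.11 says the number under the mBOIN design alone "is expected to lie between 30 to 40 subjects in realistic scenarios", with about 49 optional additional subjects. By the data cut in Section 2.1.4.1, 18 had been evaluated for DLTs. Monotherapy Expansion: 3 × 20 = 60. Combination: 6 + 20 = 26 to 12 + 20 = 32.

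**The plan's own totals.** Expansion: 60 + 12 + 20 = 92, which matches. With a run-in of 6 it is 86. Escalation: 30 + 49 = 79 to 40 + 49 = 89, consistent with up to 90. The documents give no operating characteristics for the stopping criterion, so there is none to reproduce.

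**Formula.** Subjects with an event needed = 0.33 × N, rounded up. Highest attainable rate = exposed / N, assuming no Grade 3 or higher CRS/ICANS on GEN3009 alone.

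| Subjects counted | N | Needed | Exposed to GEN3013 | Highest rate |
|---|---|---|---|---|
| Escalation 90 + Expansion 92 | 182 | 61 | 32 | 17.6% |
| Escalation 40 + Expansion 92 | 132 | 44 | 32 | 24.2% |
| Escalation 30 + Expansion 92 | 122 | 41 | 32 | 26.2% |
| Escalation 18 + Expansion 92 | 110 | 37 | 32 | 29.1% |
| Expansion only, run-in of 12 | 92 | 31 | 32 | 34.8% |
| Expansion only, run-in of 6 | 86 | 29 | 26 | 30.2% |
| Combination only | 32 | 11 | 32 | 100% |

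For the first row, 0.33 × 182 = 60.06, so 61 are needed, and 32/182 = 17.6%. Using exactly one third instead of 0.33 leaves every count in the table unchanged.

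**Expansion only, N = 92.** The criterion needs 31/32 = 96.9% of combination subjects. The exact binomial chance of that is 0.0002 at an assumed true rate of 70% and 0.16 at 90%.

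**General limit.** With 32 exposed, N can be at most 96 (0.33 × 96 = 31.7, so 32 are needed; at 97, 33 are needed). At most 96 − 32 = 64 unexposed subjects can be counted before the criterion is out of reach. With 12 exposed the limit is 24.

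**During the run-in, before any monotherapy Expansion.** Escalation 18 + run-in 6 needs 8 of 6, and escalation 30 + run-in 12 needs 14 of 12. Both are impossible. Escalation 18 + run-in 12 needs 10 of 12.

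**If combination accrual ran far ahead.** With 32 combination subjects and no monotherapy Expansion, 30 escalation subjects give N = 62 and 21 of 32 needed (66%). Forty give N = 72 and 24 of 32 (75%). The criterion can then be met, but only at a very high event rate.

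**Combination subjects only.** The criterion becomes 4 of 12 in a run-in of 12, 7 of 20 in the later phase, or 11 of 32 overall. At 11 of 32, the chance of meeting it is 0.50 at an assumed true rate of 33% and 0.97 at 50%.

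**The case against.** The strongest reply is that Section 4.4.3 says whom the criteria cover and never says that everyone is pooled into one denominator. Section 11 says that escalation and Expansion data, and monotherapy and combination data, will in general be summarized separately. Section 10.3 ties CRS and ICANS to the combination. A sensible committee would therefore look within the combination cohort, where the criterion works. This stands in part: pooling is never written, and a cohort-level reading is reachable. But Section 11 governs reporting, and the only sentence that defines the population for the criteria draws no such line.

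A second reply is that the DMC charter may settle the matter. Sections 4.4.3 and 10.8 leave review intervals to it, and SAP Section 15 leaves the safety-monitoring analysis to it. That cannot be checked here. No passage says that the charter defines this denominator, and the SAP was written for protocol version 4.0 and does not cover the combination.

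A third reply is that other safeguards exist, and they do. Run-in DLT rules count Grade 3 or higher CRS and ICANS, except Grade 3 events improving within 48 hours (Section 7.3). Sections 7.4.3.2 and 7.4.3.4 give subject-level GEN3013 discontinuation rules. The DMC can meet ad hoc, and Section 4.4.3 has triggers based on judgement. However, the DLT rules apply to the run-in and its 28-day window, not to the 20 subjects treated afterwards.

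A reader might also infer that a cohort-level reading would make the criterion fire on one early event. The documents do not support that: they give no Grade 3 or higher CRS/ICANS rate for the combination and schedule no look at so small a number.

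**Conclusion.** Wrong as written, and it should be fixed. On the stated population, the CRS/ICANS criterion is arithmetically unreachable at planned enrolment (61 needed, 32 at risk), and remains so with only the 18 escalation subjects already evaluated (37 needed). Counting Expansion alone, it needs 31 of 32, or is impossible with a run-in of 6 (29 needed, 26 exposed). This conflicts with Sections 7.4.3.2, 7.4.3.4 and 10.3, which tie these events to the combination.

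The result rests on two assumptions: almost no Grade 3 or higher CRS/ICANS on GEN3009 alone, which the protocol supports only to date, and monotherapy accrual broadly as planned.

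A reader might infer that the trial has no working protection against severe CRS or ICANS. The documents do not support that, because the safeguards above are independent of this percentage. The IRR and neutropenia criteria do not share this exposure problem, since every subject receives GEN3009.

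**What to change.** Reconcile Section 4.4.3 with Sections 4.1, 7.4.3.2, 7.4.3.4 and 10.3. The text should state which subjects form the numerator and denominator of the CRS/ICANS criterion, in a form that the subjects at risk can reach, and when the criterion is evaluated. The DMC charter should carry the same definition. This point does not ask for a different threshold, and the choice of rule is the sponsor's. The cost is protocol wording and alignment of the charter, with no change to sample size or data collection.

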4.4.4 Trial Termination

The sponsor reserves the right to close the trial site or terminate the trial at any time for any reason at the sole discretion of the sponsor.

In addition, the investigator may initiate trial-site closure at any time, provided there is reasonable cause and sufficient notice given in advance of the intended termination. Reasons for the early closure of a trial site by the sponsor or investigator may include, but are not limited to:

- Failure of the investigator to comply with the protocol, the requirements of the IEC/IRB or local health authorities, the sponsor's procedures, or ICH Good Clinical Practice (GCP) guidelines
- Inadequate recruitment of subjects by the investigator
- Discontinuation of further trial drug development

The sponsor may, based on available data, need to discontinue further development of GEN3009 and/or the combination of GEN3009 + GEN3013. Following trial termination, the sponsor will make their best effort to provision post-trial access to GEN3009 and/or GEN3013 for those ongoing trial subjects with a potential treatment benefit, in accordance with local laws and requirements.

5 TRIAL POPULATION(S)

5.1 Inclusion Criteria

5.1.1 Dose Escalation Inclusion Criteria

Each potential subject must fulfill all of the following criteria to be enrolled in the trial.

1. Be at least 18 years of age.
2. Must sign an informed consent form (ICF) prior to any screening procedures indicating that they understand the purpose of the trial, the procedures required for the trial, and are willing to participate in the trial prior to any other trial-related assessments or procedures.
3. Criterion updated as per Amendment 1
 - 3.1 Criterion updated as per Amendment 3
 - 3.2 Criterion updated as per Amendment 5
 - 3.3 Has histologically or cytologically confirmed relapsed or refractory B-cell NHL with no available standard therapy or is not a candidate for available standard therapy, and for whom, in the opinion of the investigator, experimental therapy with GEN3009 may be beneficial. All subjects must have received at least 2 prior lines of systemic therapy, and,
 - a. For all indolent NHL (FL, MZL, and SLL) as well as aggressive NHL (DLBCL, HGBCL, and PMBCL), at least 1 of the 2 prior lines of treatment must have been a CD20-containing systemic regimen;
 - b. For MCL, subjects must have had or are otherwise ineligible for treatment with a BTK inhibitor, and;
 - c. For CLL, subjects must have received at least 1 prior line of BTK inhibitor or BCL-2 inhibitor.
4. Criterion updated as per Amendment 5
 - 4.1 Has 1 of the following B-cell NHL subtypes for the Dose Escalation:
 - a. DLBCL, de novo or histologically transformed
 - b. HGBCL ([Swerdlow et al., 2016](#))
 - c. PMBCL
 - d. FL, with advanced symptomatic disease and with a need for treatment
 - e. MCL, without leukemic manifestation
 - f. MZL, either nodal, extranodal, or mucosa associated, with a need for treatment initiation based on symptoms and/or disease burden
 - g. SLL, with a need for treatment based on symptoms and/or disease burden
 - h. CLL with active disease that needs treatment based on the International Workshop on Chronic Lymphocytic Leukemia [iwCLL] criteria) ([Hallek et al., 2018](#))
 - i. Criterion updated as per Amendment 3

5. Criterion removed as per Amendment 5
6. Criterion updated as per Amendment 5

6.1 Has measurable disease:

i. B-cell NHL:

- a. A fluorodeoxyglucose (FDG)-positron emission tomography (PET) computed tomography (CT) scan demonstrating positive lesion compatible with CT (or magnetic resonance imaging [MRI])-defined anatomical tumor sites

and

- b. A CT scan (or magnetic resonance imaging [MRI]) with involvement of ≥ 2 clearly demarcated lesions/nodes with long axis >1.5 cm and short axis >1.0 cm or 1 clearly demarcated lesion/node with a long axis >2.0 cm and a short axis ≥ 1.0 cm.

Note: Subjects who do not have FDG-avid lymphoma at screening will be eligible if they meet “criterion 5b”.

ii. CLL:

- c. $\geq 5 \times 10^9/L$ ($5,000/\mu L$) B lymphocytes in peripheral blood, or
- d. Presence of measurable lymphadenopathy and/or organomegaly

7. Has active disease for CLL: Progressive or symptomatic disease with at least 1 of the following criteria being met ([Hallek et al., 2018](#)):

- a. Evidence of progressive marrow failure as manifested by the development of, or worsening of, anemia and/or thrombocytopenia
- b. Massive (ie, ≥ 6 cm below the left costal margin) or progressive or symptomatic splenomegaly
- c. Massive nodes (ie, ≥ 10 cm in longest diameter) or progressive or symptomatic lymphadenopathy
- d. Progressive lymphocytosis with an increase of $\geq 50\%$ over a 2-month period, or lymphocyte doubling time (LDT) <6 months.
- e. Autoimmune complications including anemia or thrombocytopenia poorly responsive to corticosteroids
- f. Symptomatic or functional extranodal involvement (eg, skin, kidney, lung, spine)
- g. Disease-related symptoms as defined by any of the following:
 - i. Unintentional weight loss $\geq 10\%$ within the previous 6 months
 - ii. Significant fatigue
 - iii. Fevers $\geq 100.5^{\circ}\text{F}$ or 38.0°C for 2 or more weeks without evidence of infection.
 - iv. Night sweats for ≥ 1 month without evidence of infection.

8. Has Eastern Cooperative Oncology Group (ECOG) performance status of 0 or 1.

9. Criterion updated as per Amendment 5.

9.1 Has acceptable laboratory parameters as follows:

Parameter	Result
a. Creatinine clearance	>50 mL/min (Cockcroft-Gault) or serum creatinine $\leq 1.5 \times$ upper limit of normal (ULN) (refer to Appendix 1)
b. Serum alanine transaminase (ALT)	$\leq 2.5 \times$ upper limit of normal (ULN)
c. Serum aspartate transaminase (AST)	$\leq 2.5 \times$ ULN
d. Total bilirubin	$\leq 1.5 \times$ ULN Note: Subjects with Gilbert's syndrome may be included if total bilirubin is $\leq 3 \times$ ULN and direct bilirubin is $\leq 1.5 \times$ ULN
e. Hemoglobin	≥ 5.6 mmol/L (9.0 g/dL) Note: Without transfusion within 7 days of determination of eligibility.
f. Absolute neutrophil count	B-cell NHL : $\geq 1.0 \times 10^9$ /L (1,000/ μ L) CLL : $\geq 1.0 \times 10^9$ /L (1,000/ μ L) unless due to bone marrow involvement Note: Without growth factor support within 7 days of determination of eligibility (14 days if pegylated growth factor such as pegfilgrastim).
g. Platelet count	B-cell NHL : $\geq 75 \times 10^9$ /L (75,000/ μ L) Note: In presence of bone marrow involvement, platelets $\geq 50 \times 10^9$/L. CLL : $\geq 30 \times 10^9$ /L (30,000/ μ L) Note: Without transfusion within 7 days of determination of eligibility.
h. Coagulation Status: PT/INR/aPTT	Prothrombin time (PT)/International normalized ratio (INR)/Activated partial thromboplastin time (aPTT) $\leq 1.5 \times$ ULN

10. Criterion updated as per Amendment 3

10.1 A woman of reproductive potential must agree to use adequate contraception during the trial and for 12 months after the last GEN3009 administration. Adequate contraception is defined as highly effective methods of contraception (refer to [Appendix 12](#) for more information). In countries where 2 highly effective methods of contraception are required, both methods will be required for inclusion.

11. Criterion updated as per Amendment 3

11.1 A woman of childbearing potential must have a negative serum beta-human chorionic gonadotropin (beta-hCG) at screening.

12. A woman must agree not to donate eggs (ova, oocytes) for the purposes of assisted reproduction during the trial and for 12 months after receiving the last dose of GEN3009.

13. A man who is sexually active with a woman of childbearing potential and has not had a vasectomy must agree to use a barrier method of birth control, eg, condom only and spermicidal foam/gel/film/cream/suppository, and partner with occlusive cap (diaphragm or cervical/vault caps) with spermicidal foam/gel/film/cream/suppository, and all men must also not donate sperm during the trial and for 12 months after receiving the last dose of GEN3009.

14. Must be willing and able to adhere to the requirements and restrictions specified in the ICF and this protocol.
15. Subjects must have a life expectancy of at least 3 months.
16. **Sites in France only:** Must have a social security number or equivalent per local requirements.

